9.2. VA Norms

Note: The rate of visual development varies across patients. The table is presented as a reference only.

Table 9: VA Norms

Age	Grating acuity by TACII			Recognition Acuity	
	Normal VA (cy/cm)	logMAR	Snellen Equivalent §	Normal VA (feet)	logMAR
6m	2.4	1.097	20/260		
12m	3.2	0.972	20/190		
18m	4.8	0.796	20/130		
24m	4.8	0.796	20/130		
30m	6.5	0.664	20/94		
36m	9.8	0.486	20/63		
42m	13.0	0.363	20/47		
48m				20/32	0.2
5yo				20/25	0.10
≥6yo				20/20	0.00

¶ Normal VA with TAC [low limit of normal at 95% CI]

§ Conversion of grating acuity to Snellen equivalents is not recommended and is only provided for purposes of communication.

9.3. Visual Fields

Visual field testing will be performed by confrontation and reported as the number of quadrants (0, 1, 2, 3, or 4) with VF deficits.

9.4. Optic Disc Appearance

Optic discs will be assessed for the presence or absence of pallor and edema.

9.5. Visual Response

Primary functional outcome is based on visual acuity (VA) and is defined as the difference in VA after approximately 12 cycles of treatment. Eyes above the visual “ceiling” (0.2 logMAR below normal for age or 0.2 logMAR below a previous reliably documented VA) at baseline cannot improve and will be excluded from the analysis of visual response. A significant improvement in VA will be defined as a decrease of ≥ 0.2 logMAR (corrected for age) from baseline (pre-treatment baseline) to end of ~12 cycles of treatment. The analysis will be based on per participant outcome (rather than per eye).

A significant improvement in VA will be defined as a decrease of ≥ 0.2 logMAR from baseline (pre-treatment baseline) to end of ~12 cycles of treatment.

Ophthalmologic (Visual Acuity) Response Criteria

- Visual Responsive ≥ 0.2 logMAR improvement in VA compared to baseline
- Stable VA = does not meet criteria for Improved or Worsening VA compared to baseline
- Visual Progressive Disease ≥ 0.2 logMAR worsening compared to baseline*

* 0.2 logMAR worsening (or up to a 2-card drop in Teller Acuity) will not be considered visual progressive disease at the first on-therapy staging evaluation (at 12 weeks), if the tumor is stable or smaller on MRI. In these cases, a repeat visual acuity assessment will be required 6-12 weeks later to confirm that further visual progression is not occurring. If the repeat visual acuity is stable or improved (0.2 logMAR or less [or a 2 card drop in Teller Acuity or less] from pre-treatment baseline), the patient will remain on protocol therapy. If the visual acuity is now > 0.2 logMAR (or > 2 card drop in Teller acuity) worse from pre-treatment confirmed by a second exam, then the participant will be removed from the protocol.

Visual worsening ≥ 0.2 logMAR in the setting of possible pseudoprogression should be discussed on a case-by-case basis with the study chair. In most cases, patient may continue on study until pseudoprogression vs progression is confirmed. Corticosteroids may be considered, and a short interval repeat eye exam is recommended. If a repeat vision exam shows continued deterioration of visual function, then patient will be permanently removed from therapy and the time of progression will be the date of the initial MRI or vision exam showing progression. See section 10.4 for additional information regarding possible pseudoprogression.

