Endpoints:	Primary endpoint 
Objective response rate (CR+PR) within the first 48 weeks (12 cycles) of therapy, using RAPNO criteria Secondary endpoints: 
PFS at 12, 24 and 60 monthsBest response rate (CR+PR) within 24 cycles of therapyClinical benefit response rate (CR+PR+MR+SD) after 12 and 24 cycles of therapyPoly-ICLC-related toxicities Exploratory endpoints 
Vision response after 12 and 24 cycles of therapy defined as 0.2 logMAR or greater in acuity improvementPatient reported outcomes and quality of life measuresBiological correlatesComparison of RANO and RAPNO response determinations
Accrual Objectives:	Up to 20 participants will be enrolled to obtain a minimum of 16 evaluable participants on this study.
Study Duration:	Participants will be followed for a minimum of 5 years from treatment. Overall survival outcomes will continue to be measured up to 5 years from treatment.
Interim Analysis:	There will not be an interim analysis for efficacy.

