1. STUDY OBJECTIVES

This is a phase II, prospective, longitudinal, multi-center trial of poly-ICLC (Hiltonol ®) treatment for progressive low-grade gliomas in pediatric patients with NF1. The primary objective is to evaluate the efficacy of poly-ICLC in pediatric NF1 patients with progressive low-grade glioma (LGG) as measured by objective tumor response rate (CR+PR) within the first 48 weeks (12 cycles) of therapy.

The secondary objectives are to:

- a) Determine 12, 24 and 60 month progression free survival (PFS) in pediatric NF1 patients with progressive LGG treated with poly-ICLC.
- b) Evaluate the efficacy of poly-ICLC in pediatric NF1 patients with progressive LGG as measured by best objective tumor response rate (CR+PR) within 24 cycles of therapy.
- c) Evaluate the efficacy of poly-ICLC in pediatric NF1 patients with progressive LGG as measured by clinical benefit response rate (CR+PR+MR+SD) after 12 and 24 cycles of therapy.
- d) Assess the toxicity associated with poly-ICLC treatment in pediatric NF1 patients with LGG.

Exploratory objectives are to:

- a) Evaluate the visual outcome measures in children with progressive optic pathway gliomas treated with poly-ICLC. Visual response is defined as 0.2 logMAR or greater in acuity improvement.
- b) Evaluate patient reported outcomes and quality of life measures.
- c) Evaluate biological correlates.
- d) Compare RANO and RAPNO response determinations in this population.

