9.1. Visual Acuity (best corrected)

IMPORTANT NOTE: if the VA data at a particular visit is felt to be unreliable due to poor cooperation, testing should be repeated within 4 weeks. Only the visit believed to have yielded the most reliable data should be reported.

Teller acuity testing using TAC II cards will be attempted on all participants at all visits. All VA testing will be performed by study personnel who have undergone TAC teaching by the study team. VA testing will be performed in each eye separately at a distance of 55 cm in all participants. The tester will utilize the “Two down, one up” protocol to achieve the best visual acuity. Acuity will be reported in cycles/cm by the site and converted by the operations center to logMAR. Reasons for VA testing not being completed will be recorded.

Table 8: Visual acuity in feet and logMAR equivalents for acuity in cycles/cm

Card @ 55 cm (Cycles/cm)	VA equivalent	logMAR
26	20/24	0.06
19	20/32	0.20
13	20/47	0.36
9.8	20/63	0.49

6.5	20/94	0.66
4.8	20/130	0.80
3.2	20/190	0.97
2.4	20/260	1.10
1.6	20/380	1.27
1.3	20/470	1.36
0.86	20/710	1.54
0.64	20/960	1.67
0.43	20/1400	1.84
0.32	20/1900	1.97

HOTV will be attempted on participants who are old enough. HOTV will be performed using the PEDIG ATS-HOTV computerized protocol in each eye separately at a recommended testing distance of 3 meters in all participants. Acuity will be reported in logMAR. Reasons for VA testing not being completed will be recorded.

For primary analysis, the VA endpoint will be the difference between best-corrected VA at baseline and at approximately 1 year (i.e., at the post-cycle 12 assessment).

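### Section 9.5 defines visual improvement both with and without age correction; the uncorrected rule can score a Teller-tested infant or toddler eye with an unchanged deficit for age as a responder

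*Combined protocol and SAP*

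**What the plan says.** Section 9.5 gives the improvement rule in two consecutive paragraphs. The first asks for a decrease of at least "0.2 logMAR (corrected for age) from baseline (pre-treatment baseline) to end of ~12 cycles of treatment". The second asks for a decrease of at least "0.2 logMAR from baseline (pre-treatment baseline) to end of ~12 cycles of treatment", with no mention of age. The response list that follows defines a visual responder by a gain of at least "0.2 logMAR improvement in VA compared to baseline". The synopsis has "Vision response after 12 and 24 cycles of therapy defined as 0.2 logMAR or greater in acuity" improvement, and Section 1 says "Visual response is defined as 0.2 logMAR or greater in acuity improvement". None of these three mentions age.

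The first paragraph of 9.5 also excludes eyes that are too good at baseline to improve. The ceiling is set at "0.2 logMAR below normal for age or 0.2 logMAR below a previous reliably documented VA". Visual progression is at least "0.2 logMAR worsening compared to baseline".

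Table 9 (Section 9.2) is the only set of age norms in the protocol. It is labelled as a reference only, and its grating values are low limits of normal. No text says how an age correction is to be calculated. Section 9.1 has Teller testing attempted for every participant at every visit, and Section 3.1 sets no lower age limit.

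**The concern.** Two analysts following the protocol could report different visual response rates from the same data. The difference is not neutral. Grating acuity improves with age in early childhood, so a raw gain of 0.2 logMAR may reflect maturation only. In a single-arm trial there is no control group to separate maturation from drug effect; the age correction is the only device in the plan that could do it. The ceiling does not serve this purpose. It applies once, at baseline, to decide which eyes are analysed, and does not adjust the follow-up value.

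**Working it through.** **Inputs.** Table 9 grating norms (logMAR) at 6, 12, 18, 24, 30, 36 and 42 months: 1.097, 0.972, 0.796, 0.796, 0.664, 0.486, 0.363. Table 8 gives the logMAR value of each Teller card. Twelve cycles of 28 days are 48 weeks, about 11.0 months; Section 9.1 says about 1 year.

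**Reproducing the tables.** logMAR = log10(30 / cycles per cm) returns all seven Table 9 grating norms to three decimals (for example log10(30/2.4) = 1.097) and all 14 Table 8 values to rounding.

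**Movement of the norm.** An eye whose deficit (acuity minus norm) is unchanged shows a raw gain of norm(baseline age) − norm(follow-up age). The 48-week column uses linear interpolation.

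| Baseline age (months) | Over 12 months | Over 48 weeks | Reaches 0.2? |
|---|---|---|---|
| 6 | 1.097 − 0.796 = 0.301 | 0.273 | yes |
| 12 | 0.972 − 0.796 = 0.176 | 0.176 | no |
| 18 | 0.796 − 0.664 = 0.132 | 0.111 | no |
| 24 | 0.796 − 0.486 = 0.310 | 0.281 | yes |
| 30 | 0.664 − 0.363 = 0.301 | 0.281 | yes |

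With interpolation and follow-up limited to 42 months, the movement is at least 0.2 for baselines of 6.0-10.8 and 20.3-30.0 months at a 12-month interval. At 48 weeks the bands are 6.0-10.8 and 21.3-31.0 months. The synopsis also applies the rule at 24 cycles. Over 24 months the norm moves 0.433 (6 to 30 months), 0.486 (12 to 36) and 0.433 (18 to 42).

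**On actual cards.** One-card steps in Table 8 are 0.09-0.18 logMAR and two-card steps 0.26-0.31, so the uncorrected rule is met by two cards.

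**Worked example.**
- At 24 months the norm is 0.796, so the norm-based ceiling is 0.796 + 0.2 = 0.996. An eye reading 2.4 cycles/cm (1.10) is below it and is analysed. Deficit: 1.10 − 0.796 = 0.304.
- At 36 months it reads 4.8 cycles/cm (0.80). Deficit: 0.80 − 0.486 = 0.314.
- Raw gain: 1.10 − 0.80 = 0.30, a responder.
- Corrected gain: 0.304 − 0.314 = −0.01, not a responder.
- At 48 weeks the corrected gain would be 0.30 − 0.281 = 0.02, with the same classification.

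**What the corrected rule demands.** The mildest includable eyes at 6, 24 and 30 months read 1.36, 1.10 and 0.97. Three cards are not enough: from 1.10 to 0.66 the raw gain is 0.44 and the corrected gain 0.44 − 0.310 = 0.13. Four cards bring these eyes to 0.80, 0.49 and 0.36, against 12-month norms of 0.796, 0.486 and 0.363.

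**The case against.** The strongest reply is that the age-corrected paragraph carries the operational detail (the ceiling and the per-participant analysis), so the shorter statements can be read as abbreviations. That is a natural reading, but the text does not say so, and the response list in the same section omits the correction. Even on this reading the method is still undefined.

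A second reply is that almost nobody is exposed. That stands. A child must have an optic pathway glioma that has progressed after prior medical treatment, an eye below the ceiling, Teller results at both visits, and an age in one of two narrow bands, in a trial of at most 20.

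Third, Table 9 is a reference-only low limit of normal, and keeping pace with age may be clinically worthwhile in a progressing tumour. Both points stand. They argue for showing the raw change as well, not for two rules under one name.

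Several stronger readings are tempting but unsupported:
- A reader might infer that the reported visual response rate will be inflated. The example needs an impaired eye to mature at close to the norm's rate: a two-card gain is 0.26/0.310 = 0.84 to 0.31/0.301 = 1.03 of the norm's movement. The documents do not say how often that happens.
- A reader might infer that all young children are affected. At 12 cycles, baselines of about 11 to 20 months are not.
- A reader might extend the point to HOTV. The recognition norms move only 0.10 a year from 48 months, so those pairs are not exposed at 12 cycles.
- A reader might count Section 9.1 as a further contradiction. It says "the VA endpoint will be the difference between best-corrected VA at baseline and at approximately 1 year", which names a variable and sets no response threshold.

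**Conclusion.** The conflict is in the current text, and the uncorrected rule can label an eye with no gain for age as a visual responder at 12 cycles. This holds for below-ceiling, Teller-tested eyes from baselines of about 6-11 or 21-30 months. It rests on Table 9 as the norm, linear interpolation between its ages, and a constant logMAR deficit as the meaning of no change for age.

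The consequence is limited. Visual response is exploratory in Section 1 and the synopsis. Section 14 lists visual acuity among the secondary endpoints, but with no hypothesis test, and Section 14.3 describes the analyses as largely descriptive. The primary objective-response test is untouched, and removal from therapy already runs on raw change. The reason to act is that a descriptive rate still needs one definition, and this one is cheap to settle before analysis.

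**What to change.** Delete the uncorrected sentence in 9.5 and make the age-corrected definition govern visual response in the 9.5 list, the synopsis and Section 1, at 12 and 24 cycles. Define it as the change in deviation from the normal-for-age value, using the same test at both visits. The 9.5 ceiling already needs such a value. Either lift the reference-only label from Table 9 for this purpose or name another norm, and state what applies to Teller results after 42 months, where the grating norms stop. Report the raw change alongside, descriptively.

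Leave Visual Progressive Disease and removal on raw change. If these were corrected too, an eye with flat acuity would show 0.30-0.31 worsening at 12 months from baselines of 6, 24 or 30 months and could be taken off therapy. The norm moves at most 0.08 by 12 weeks, 0.16 by 24 weeks and 0.23 by 36 weeks, so this could begin at the cycle 9 examination.

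The cost is protocol wording and one derived variable from data already collected. There are two real downsides. Fewer young children will count as responders, and at 12 months the mildest includable eyes at baselines of 6, 24 and 30 months must reach about the Table 9 low limit of normal. Response and progression will also sit on different scales, so the stable category can hold both a raw gain of 0.44 and a flat eye that has fallen 0.31 behind its age norm.

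A minor clarification, of low severity: in the 9.5 footnote, a two-card Teller drop (0.26-0.31 logMAR) at the repeat examination literally meets both the wording for staying on therapy and the wording for removal. State that the card limit applies to Teller results and the 0.2 logMAR limit to HOTV, which is the natural reading already.

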10. IMAGING PARAMETERS AND RESPONSE CRITERIA

10.1. General Considerations

Patients with NF1-associated LGG may have multiple lesions; typically, however, decision to treat is based on a clinical or radiographic progression of a single lesion. If multiple measurable lesions are present, ONE should be selected as the “target” lesion. The overall response assessment takes into account response in the **target lesion only**. The target lesion should be the same as the target tumor identified for eligibility confirmation (section 3.1), and should be selected on the basis of clinical relevance, size, and suitability for accurate repeated measurements. The lower

size limit of the target lesion should be at least twice the thickness of the slices showing the tumor to decrease the partial volume effect (e.g., 8 mm lesion for a 4 mm slice).

Up to 2 additional lesions may be followed as non-target lesions. Any change in size of non-target lesions should be noted. The response to non-target lesions will be evaluated independently of the response of the target lesion but will not be included in the primary response assessment.

Development of new lesions is not considered progressive disease for this study.

10.2. Measurement of Effect

Methods for Evaluation of Measurable Disease: Whole Brain MRI With and Without Contrast. For patients with optic pathway gliomas, orbital cuts are necessary. For target tumors outside the brain (i.e. spinal cord), clinically appropriate imaging modalities may be added or substituted.

The following section describes the methodology.

1. For MRI imaging, the longest diameter can be measured from the axial plane or the plane in which the tumor is best seen or measured, provided the same plane is used in follow-up. This longest measurement of the tumor is referred to as the width (W).
2. The perpendicular measurements should be determined – transverse (T) measurement, perpendicular to the width in the selected plane.
3. The cystic components of a tumor are considered in tumor measurements.
4. Leptomeningeal tumor spread is usually not a target lesion, and usually cannot be measured accurately. Presence and location of leptomeningeal tumor spread should be noted and change in extent/thickness assessed on follow up studies.

Imaging Response Criteria for Target Lesion

Response criteria are assessed in 2 dimensions – the product of W x T. Baseline measurements should include the longest diameter and the longest perpendicular diameter. These same 2 measurements should then be followed throughout therapy.

For example, if anterior-posterior (AP) is the longest diameter and crano-caudal (CC) is the longest perpendicular diameter, and then AP and CC should be followed throughout therapy for that lesion.

To assess response/progression/relapse, the ratio is calculated:

$$\mathbf{W \times T \text{ (current scan)} / W \times T \text{ (reference scan)}}$$

Imaging: Standard MRI evaluation is required for disease evaluation as per institutional imaging parameters. Both 1.5T and 3.0 T magnets are acceptable.

Additional Imaging Studies: MR diffusion-weighted imaging (DWI), dynamic contrast-enhanced (DCE), and T1 permeability perfusion MRI, and MR spectroscopy (MRS) are recommended as

part of standard of care at each evaluation period. The data obtained from these studies will be correlated with patient response and outcome.

The following sequences incorporate the standard CNS imaging protocol. Institutional brain tumor or solid tumor imaging protocols can be substituted as long as similar disease evaluation is possible.

10.3. Imaging Sequences

Table 10: Imaging Sequences 1.5 T

Sequence	Slice Thickness	TR (ms)	TE (ms)	TI (ms)	Directions	B ₀	FOV (cm)	Matrix
Sagittal T1	5 mm skip 1	400	9				22	256 x 256
Axial FSE T2	2 mm skip 0	3800	102				20	256 x 256
Axial T2 FLAIR	4 mm skip 0	10000	160	2200			20	256 x 224
Axial diffusion	2.5 mm skip 0				12-30	1000	26	128 x 128 single shot
Sagittal T2	3 mm skip 1	3800	102				22	256 x 256
Axial MPGR	4 mm skip 0							
Axial T1	4 mm skip 0	500	min				20	320 x 224
Axial T1 with Contrast	4 mm skip 0	500	min				20	320 x 224
Sagittal T1 FSPGR with contrast	1.5 mm skip 0		min, flip angle 15				24	256 x 256
T1 permeability perfusion sequence	5 mm skip 0 (See below)							
Single-voxel MR Spectroscopy PRESS	Volume: 15x15x15 mm ³	1500 ms	35ms					

Table 11: Imaging Sequences 3.0 T

Sequence	Slice Thickness	TR (ms)	TE (ms)	Directions
Sagittal T1 MPRAGE	1.0 mm skip 0	2530		
Sagittal T2	3.0 mm skip 1.0 mm			
Axial T2	2.5 mm no skip	11730	91	
Axial T2 FLAIR	4 mm, no skip	9000	137	
Axial diffusion	2 skip 0	9100	88	30
Sagittal MPRAGE	1.0 mm no skip			
Axial T1 post contrast	4.0 mm skip 0	650	9.7	
Axial SWI	1.25 mm no skip			

T1 permeability perfusion sequence	5 mm skip 0 (See Below)			
Single-voxel MR Spectroscopy PRESS	Volume: 15x15x15 mm ³	2000 ms	35ms	

T1 Permeability Imaging

T1 permeability should begin with a set of T1 maps with flip angles of 2, 5, 10, and 15 followed by the T1 permeability sequence. After the T1 map sequence with 15-degree flip angle, start the T1 permeability series and 20 seconds into it inject 0.1 mmol/kg of intravenous contrast. See below.

Table 12: 3D T1W Specifications for T1 Maps and Dynamic Series

Sequence Type	Spoiled Gradient Echo
Imaging mode	3D
Slice orientation	Axial
Frequency direction	A/P
Phase direction	R/L
FOV - frequency	220 mm
FOV - phase	220 mm
Matrix - frequency	256
Matrix - phase	160-192
In-plane resolution	≤ 1 mm
Fat-suppression	No Fat Sat
TR	~4 msec
TE	Less than 2 msec or min full
TI (STIR sequence)	N/A
Flip Angle	DCE -15 degrees; T1 maps - 2, 5, 10 and 15
Slice thickness (acquired, not interpolated)	5mm, maximum 6mm
Number of slices	Minimum 10 prior to zero fill
Slice Gap	No gap
Parallel imaging factor	≤ 2
Number of averages	1 for DCE, 2 for T1 maps
k-space ordering	standard, non-centric
Temporal Resolution of "T1 DCE": (seconds per phase/measurement)	≤ 6 seconds
"T1 DCE" imaging duration	≥ 5 minutes

Table 13: T1 Maps/DCE

Series Name	Sequence	Flip Angle	Notes
T1 map15	3D fast GRE	15 degrees	Axial, 2 NEX
T1 map10	3D fast GRE	10 degrees	Axial, 2 NEX
T1 map05	3D fast GRE	5 degrees	Axial, 2 NEX
T1 map02	3D fast GRE	2 degrees	Axial, 2 NEX
T1 DCE	Dynamic Series, 3D fast GRE	15 degrees	Axial, 1 NEX, inject 20 sec into this

10.4. Imaging Response Assessment

The overall response assessment takes into account response in the target lesion ONLY. The response in the non-target lesions will be evaluated independently from the response for the TARGET lesion.

Note: Participants with a global deterioration of health status requiring discontinuation of treatment without objective evidence of disease progression at that time should be reported as "*symptomatic deterioration*." Every effort should be made to document the objective progression even after discontinuation of treatment.

Evaluation of Target Lesion

- **Complete Response (CR)** Complete disappearance of the target lesion on T2 weighted and T2 weighted fluid attenuated inversion recovery (FLAIR) imaging and contrast imaging using baseline MRI or best recorded response for comparison. Overall, the patient must be clinically stable or have improved on physical examination and functional or neurological assessment.
- **Partial Response (PR):** a 50% or greater reduction in the target lesion on T2 weighted and T2 weighted-FLAIR imaging using the baseline MRI for comparison. Overall, the patient must be clinically stable or have improved on physical examination and functional or neurological assessment.
- **Minor Response (MR):** a 25-49% reduction in the target lesion on T2-weighted and T2-weighted-fluid-attenuated inversion recovery imaging using the baseline MRI or best recorded response for comparison. Overall, the patient must be clinically stable or have improved on physical examination and functional or neurological assessment.
- **Stable Disease (SD):** An increase or a decrease in the target lesion that is not sufficient to qualify as progressive disease or responsive disease (partial response or minor response), respectively. Overall, the patient must be clinically stable or have improved on physical examination and functional or neurological assessment.
- **Progressive Disease (PD):** A greater than 25% increase in the target lesion, usually assessed on T2-weighted and T2-weighted FLAIR using the baseline MRI or best recorded response for comparison. A determination of PD may be deferred if pseudoprogression is suspected (see "**Consideration for possible pseudoprogression / treatment-related effect**" below). Given the possibility of pseudoprogression with immunotherapy, a short interval MRI at the discretion of the treating physician is recommended for participants with PD.

Note that the appearance of new discrete lesions should be noted, but is not considered progressive disease. See section 3.5 regarding off therapy and off study criteria for patients requiring therapy for new or progressive non-target lesions.

See section 9.5 for definition of visual progressive disease. For progressive disease by clinical criteria, confirmatory imaging studies should be obtained when feasible.

- **Unevaluable (UN):** Assessment of target lesion cannot be made due to insufficient or unevaluable data. In this case, a concise explanation must be given.

